This study will be performed as a pragmatic controlled clinical trial. Patients fitting inclusion criteria who are admitted to the Vanderbilt University Adult Hospital will be enrolled in this study. Individual patient-level quasi-randomization will be employed. Odd-numbered MRNs will be assigned to the prone positioning and even-numbered MRNs will be assigned to the usual care arm. COVID-19 admissions will be reviewed during the daily COVID huddle, and appropriate study team personnel will facilitate protocol execution, working with the local providers/units.

5. Study Procedures

The study procedures in place involve treatment assignment, as well as electronic data capture. Day zero will be defined as the day of enrollment and treatment assignment. Data will originate from the electronic medical record for all patients, as well as from non-invasive patient wearable positioning sensors for a random subset to ensure protocol fidelity. Patients will be assigned to either one of the two comparator arms. Patients and providers will necessarily be unblinded, but outcomes will be analyzed by a blind assessor. Study arm assignment and the corresponding protocol will be discussed at the beginning of each day during the daily COVID-19 huddle. Workflow will include an initial run in period as we expect implementation uptake to take time. Patients enrolled during this ramp-up and optimization period will be allocated to

Study Protocol: Version 7.0 - October 29, 2020

Full Study Title: Pragmatic Trial Exploring Impact of Patient Positioning in the Management of Patients Infected with COVID19: Supine vs. Prone

Primary Investigator: [name], MSc

either the prone or usual care group as appropriate, but their data will not be included in the final analysis.

Comparator Arm A: COVID-positive patients who require supplemental oxygen, but are not yet mechanically ventilated, will be encouraged to lay in a completely prone position for as much time as is tolerable during hospitalization. Guidelines to ensure standardization include the following:

- Instructions to care-giving teams on how to frame the prone positioning ask to patients
- Request that clinical team provide reminders to the patient to prone if they are able (as feasible given workloads)
 - Suggest putting a pillow under pelvis/abdomen and under the lower legs to alleviate lower back strain
 - Suggest listening to podcast, music, or audiobook

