The scale remains ordinal in nature. We will use the approach of last value carried forward for patients who are not observed for the full five days. Patients discharged home will be at the bottom end of the scale (generally room air) while those who die will be scored the worst possible outcome. Patients discharged to long term care facility or similar will have their oxygen needs at transfer noted as their final requirements. We do not expect many patients to fall into this category since the endpoint is being measured relatively close in time to the intervention (5 days), and transfer is likely to occur after much later in the clinical course.

Study Protocol: Version 7.0 - October 29, 2020

Full Study Title: Pragmatic Trial Exploring Impact of Patient Positioning in the Management of Patients Infected with COVID19: Supine vs. Prone

Primary Investigator: [name], MSc

In the absence of any pre-existing information about our ordinal outcome, and rapidly evolving statistical capabilities to analyze these data being led by our group and others around the world, we describe a traditional analytical approach with associated sample size considerations. We recognize that in the coming weeks new methods will greatly improve the statistical efficiency of these trials and allow us to draw conclusions from fewer patients enrolled. Importantly, evolving approaches will be Bayesian in nature, which allows for early looks at the data so that we can understand the measurement properties of our ordinal scale and the impact of prone positioning and adjust as necessary.

We will use a proportional odds model to compare outcomes between study groups. Because it is possible that oxygen needs at day 5 are influenced by baseline oxygen requirements, we will adjust for baseline. This will answer the question: ‘for two patients who have the same oxygen requirements at baseline, will the patient who is in the prone positioning arm have lower oxygen requirements at day 5 than the person in the alternative arm’. Our final model will also adjust for age, BMI, smoking status, and baseline comorbidities.

Secondary analyses that involve continuous variables will generally use a proportional odds model with death always coded as ‘worst outcome plus one’. This will prevent bias associated with early death in COVID-19, which is known to have a high mortality right among hospitalized patients. For binary outcomes, a logistic model will be used.

Sample size considerations

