The primary endpoint as an ordinal variable that quantifies provision of oxygen as the main measure of clinical status measured on the fifth day of enrollment. The basis of the outcome is the World Health Organization Ordinal Covid-19 Outcome Scale, and this has been combined with data concerning the intensity of oxygen requirements. Patients are first ranked by categories of oxygenation strategies from the least invasive to the most invasive. Then, within rank, they are assigned a score based on the oxygen delivery settings as follows:

- Death
- ECMO
- Mechanical ventilation (ranked by mean FIO₂ for the day)
- Non-invasive ventilation such as BIPAP (ranked by mean FIO₂ for the day)
- High flow nasal cannula (ranked by mean FIO₂ for the day, estimated from the %FIO₂ recorded on the device)
- Standard nasal cannula (ranked by mean FIO₂ for the day, FIO₂ on standard nasal cannula or face mask is estimated as $21 + 3 \times$ liters per minute (LPM) O₂ flow)
- Room air

To minimize missingness on this primary outcome, we use the approach of last value carried forward for patients who are not observed for the full five days. Patients discharged home are at the bottom end of the scale (generally room air) while those who die will be scored the worst possible outcome. Patients discharged to a long-term care facility or similar have their oxygen needs at transfer recorded as their final requirements. Not many patients are expected in this category because the endpoint is being measured relatively close in time to the intervention (5 days), and when transfers occur in this population, they are likely to occur after much later in the clinical course.

Secondary Endpoints:

The secondary endpoint is constructed the same way as the primary endpoint, but measured on each of the first five days of randomization.

Exploratory Endpoints:

A number of exploratory endpoints have been proposed for this trial, and additional outcome may be proposed as understanding of the underlying disease and treatment course evolves. Below, we list the pre specified exploratory outcomes. For newly proposed endpoints, the analytical approaches will generally be similar to those described below.

- Length of Stay
- ICU Length of Stay
- Intubation yes/no

- Ventilator-free days (VFDs) to 28 days, calculated as a backwards count of whole days from day 28 to the last day in receipt of mechanical ventilation.
- Oxygen Levels
 - Maximum FIO2 for each day 1-5 after enrollment

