We will describe fidelity of the intervention using the ‘dose’ of proning. This will be characterized primarily using nursing estimates of the number of hours a patient spent prone during a shift. Briefly, each nursing shift lasts for 12 hours, running from 7am to 7pm. After each shift, the nurse was asked to estimate for how many hours enrolled participants were prone, regardless of which study arm they were in. We will characterize the time spent prone as estimated total time, proportion of time, average time per shift. We note that a supplementary study included more formal objective measurements of proning. The accuracy of the nursing estimate of proning may be estimable and reported as a result of that supplementary study.

Main Analysis

Our main analysis will be a covariate-adjusted proportional odds (PO) regression model with the main predictor being group assignment. Suppose the outcome Y_i for participant i can take one of the J ordered level of responses $j = 1, 2; \dots; J$. The PO logistic regression models the logit as a linear function of the randomization groups and a set of pre-specified covariates:

$$\text{Log} \left(\frac{\Pr(Y \leq j)}{1 - \Pr(Y \leq j)} \right) = \alpha_j + \beta_1 X_1 + \dots + \beta_p X_p, \quad \text{for } j = 1, 2, \dots, J - 1 \quad (1)$$

where X_1 is an indicator variable that defines the treatment groups, X_2 represents the important baseline covariate of severity, and the remaining X_s represent the additional covariates.

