In the proportional odds model we assume that the relationship between each level in the outcome variable is proportional, so the effect that describes the relationship between the lowest category versus all higher categories of the outcome variable is the same as the relationship that describes the next lowest category and all higher categories. The proportionality assumptions will be explored graphically e.g. the logit of the empirical cumulative distribution function of the outcome should be parallel among categories of covariate X_j , and a partially proportional odds model may be pursued. The covariates that will be included in the model are those listed in the descriptive analyses, which include the important variable of baseline severity. Duplication of comorbidity variables will be avoided; only the Elixhauser score will be used. To check other model assumptions, the approaches described in Regression Modeling Strategies (Harrell 2015, 2nd ed.) will be used, i.e. we will assess the model fits, residual plots, partial effect plots, and/or anova plots (Wald minus the d.f.) will be displayed. Model results will be summarized with point estimates, 95% C.I., and p-values displayed in tabular form or graphically, along with model fit statistics.

Secondary Analysis

We have specified a single primary endpoint, and so we are not adjusting for multiplicity. Since our secondary endpoint should be more sensitive than the primary for changes in the outcomes, we are not employing a gatekeeping strategy. We will proceed with the secondary analysis regardless. With up to 5 outcome measurements per patient, a proportional odds model will be specified to include the random effect of patient and we will include number of days since enrollment. We will additionally include the time by treatment interaction to determine whether there is a differential treatment effect of proning over the observational window.

For exploratory outcomes, binary outcomes will be modeled assuming a logit link function, and ordinal and discrete outcomes will be modeled using a proportional odds model. Similar approaches will be used to modeling as for the main analyses.

Missingness

We do not expect missingness on our primary outcome. There may be missingness on covariates or on secondary or exploratory outcomes. We will not exclude cases with missing covariates. We will use multiple imputation with predicted mean matching. Cases with missing outcomes may also have the outcomes imputed

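### The secondary repeated-measures model does not list baseline oxygen severity, and the SAP leaves the coding of day and the reported treatment contrast open

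*SAP*

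**What the plan says.** The SAP (Endpoints, Secondary Endpoints) defines one secondary endpoint: "The secondary endpoint is constructed the same way as the primary endpoint, but measured on each of the first five days of randomization". Its model is in Statistical Approach, Secondary Analysis: "a proportional odds model will be specified to include the random effect of patient and we will include number of days since enrollment". The next sentence reads "We will additionally include the time by treatment interaction to determine whether there is a differential treatment effect of proning over the observational window". No covariate is named there.

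For the primary model, SAP Main Analysis says that "X_2 represents the important baseline covariate of severity" and then "The covariates that will be included in the model are those listed in the descriptive analyses, which include the important variable of baseline severity". Oxygen status at enrollment is in that descriptive list, in three levels (low flow, high flow, non-invasive ventilation). Protocol section 8 gives the reason for the day-5 analysis: "Because it is possible that oxygen needs at day 5 are influenced by baseline oxygen requirements, we will adjust for baseline". The protocol's sentence on secondary analyses covers the model family and the coding of death, and says nothing about covariates.

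On the time origin, Protocol section 5 says "Day zero will be defined as the day of enrollment and treatment assignment". Neither document says whether day is numeric or categorical, whether it is centred, or which treatment contrast is the secondary result.

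**The concern.** Where the SAP wants main-model methods reused, it says so: for exploratory outcomes in the second paragraph of Secondary Analysis, and for subgroups in their own section. The paragraph on the secondary endpoint has no such sentence. A statistician who follows it literally fits a model without baseline severity.

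Three things are at stake.

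- **Precision.** The SAP expects this endpoint to be more sensitive than the primary and will analyse it whatever the primary shows. Leaving out a covariate that is already collected works against that aim.
- **Chance imbalance.** Allocation is by odd or even record number, and no stratification by severity is described. Model adjustment is the only stated protection against an uneven baseline. A patient random intercept models the spread between patients; it does not remove a difference in baseline between arms.
- **The reported effect.** With a numeric day term counted from enrollment plus an interaction, the treatment row of the output refers to day 0. If benefit builds up over days, that row can sit near zero while the later effect is real.

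**Working it through.** **The plan's own figure.** The documents give no power figure for the secondary model. For the primary they state 80% power for OR 1.6 with 250 per arm. The Whitehead formula is N = 12(z_a + z_b)² / [(ln OR)²(1 − Σp̄³)]. I used two-sided alpha 0.05 (assumed; the documents do not state it) and the day-5 distribution in Protocol section 8 (1, 5, 14, 30, 10, 40%), averaged over arms. This gives N = 484 for 80% power, and 81.2% power at N = 500. The stated figure is reproduced to within about one point, and nothing below changes it.

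**What the treatment row means.** With numeric, uncentred day, log OR(t) = b_trt + t·b_int. At t = 0 this is b_trt. With linear day, the average over days 1-5 is b_trt + 3·b_int, the day-3 contrast.

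**Approximate precision on the latent scale.** With n = 250 per arm, linear day 1-5, between-patient variance s_b², and baseline explaining a share R² of it:

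Var(t) = (2/n)[s_b²(1 − R²) + (π²/3)(1/5 + (t − 3)²/10)]

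The intra-patient correlation (ICC) and R² are assumptions.

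| ICC | Unadjusted SE, day 0 | Unadjusted SE, day 3 | Ratio | Day-3 variance after adjustment, R² = 25% / 50% / 75% |
|---|---|---|---|---|
| 0.50 | 0.235 | 0.178 | 1.32 | 79% / 58% / 38% |
| 0.70 | 0.301 | 0.258 | 1.16 | 77% / 54% / 31% |
| 0.85 | 0.422 | 0.393 | 1.07 | 76% / 52% / 28% |

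**Simulation of the model itself.** A random-intercept proportional odds model was fitted by quadrature: N = 500, 80 runs, true log OR 0 at day 0 rising linearly to ln 1.6 = 0.47 at day 5, moderate baseline effect. The fitted patient SD was 2.31 without baseline and 1.98 with it, so baseline explained 1 − 1.98²/2.31² = 27% of between-patient variance.

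| Contrast | Mean log OR, unadjusted | SE, unadjusted | SE, adjusted | Reduction |
|---|---|---|---|---|
| Day 0 | −0.01 | 0.280 | 0.259 | 7.5% |
| Day 3 | 0.27 | 0.224 | 0.197 | 12.1% |
| Day 5 | 0.46 | 0.254 | 0.230 | 9.4% |

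Putting 2.31 and 1.98 into the formula predicts reductions of 8.2%, 12.6% and 10.2%, so the two methods agree. Day-5 power was 51% with and without baseline. Its Monte Carlo error is √(0.51 × 0.49/80) = 5.6 points, so a modest gain could be hidden. The unadjusted treatment row averaged −0.01 while the day-5 contrast averaged 0.46.

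**Chance imbalance.** At N = 550, a baseline difference of one standard error is 2/√550 = 0.085 SD. The planned effect on the same scale is ln 1.6/1.814 = 0.259 SD. With an assumed baseline-score correlation of 0.5 to 0.7, the shift in an unadjusted estimate is 0.5 × 0.085/0.259 = 16% to 0.7 × 0.085/0.259 = 23% of the planned effect, in either direction.

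**The case against.** The strongest reply is that silence is not exclusion. The secondary text does not name the treatment main effect either, so its list is plainly not exhaustive and may only state what repeated measures add to the main model. The secondary endpoint is built like the primary, and the protocol writes adjustment for enrollment status into the primary outcome definition. The sentence on reusing main-model approaches stands under the Secondary Analysis heading, though in the exploratory paragraph. This stands in part. A reader might infer that the SAP deliberately drops baseline from the secondary analysis; the documents do not support that. But carry-over is not stated either, and the SAP aims to let an independent statistician follow it.

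The day-0 point is conditional. It fails if day is categorical or centred, and the SAP does not say that the treatment row will be reported. Its stated question is the interaction, and centring does not change that test. Nor can one say that day 0 precedes all proning: it is the day of assignment, so proning could begin then. If the first five days include day 0, that row lies inside the window.

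A reader might also infer a large power loss or a biased odds ratio. Neither is shown. Large gains need a strong baseline effect that the documents do not quantify; the protocol calls the influence only possible. If allocation is as good as random, omitting baseline costs precision and leaves chance imbalance, without systematic bias. Finally, matching covariates would not make the primary and secondary odds ratios directly comparable, because only the secondary is conditional on a patient effect.

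**Conclusion.** The point holds as an under-specification with a real cost if the text is followed literally. The listed model omits a covariate that the SAP itself calls important and already collects. The result is lower precision and uncorrected chance imbalance. With baseline explaining about a quarter of between-patient variance, standard errors fall roughly 8-12%. A weaker association would give less and a stronger one more, and the documents cannot settle which. No gain in day-5 power was visible, so none should be claimed. The day-0 reading applies only under numeric, uncentred day with the treatment row taken as the result. Not naming the reported contrast is a gap under any coding. The primary analysis and the planned 500 and 550 patients are untouched.

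**What to change.** Add to SAP Secondary Analysis:

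*The secondary model includes treatment, ordinal oxygen status at enrollment, the other primary-model covariates, day and the day-by-treatment interaction, with a random patient effect. If the full covariate set does not converge, enrollment oxygen status is retained as a minimum. Outcome days are days 1 to 5, with day 0 as enrollment; day is entered as [numeric or categorical, to be stated]. We report the treatment contrast on each day and its average over days 1-5, alongside the day-by-treatment test. The day-0 coefficient is not reported as the treatment effect.*

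The cost is these few sentences and a somewhat more complex fit, since the full covariate list with a random effect and a finely ranked outcome may be slow or unstable; the fallback covers that. No new data are needed.

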and by group. Groups will not be formally compared used statistical tests; differences and confidence intervals of differences may be reported. All categorical variables will be described using frequencies and proportions, and continuous variables will be described using mean, standard deviation, and percentiles (i.e. 25th , 50th , 75th). Missingness will be recorded for each variable. To further assess the distribution of variables, graphical summaries will be displayed using box-plots, dot-plots, violin-plots, and/or histograms. At a minimum, the following baseline variables will be described:

- Age (years)
- Sex (Male, Female, Not reported)
- BMI – kg/m²
 - Obesity (None, Stage I BMI 30.0 -34.9; Stage II BMI 35.0 – 39.9; Stage III BMI>=40.0, Not reported)
- Race (American Indian/Alaska Native, Asian, Black/African American, White, Other, Not reported)
- Ethnicity (Hispanic or Latino, Not Hispanic or Latino, Not reported)
 - Ethnicity may be combined with race
- Elixhauser Score
- Number of coexisting conditions (None; One; Two or more)
- Coexisting conditions (Yes/No)
 - Any
 - Diabetes
 - Hypertension
 - Underlying Respiratory Disease
 - Heart Disease
 - Renal Disease
 - Malignancies
- Smoking Status (as documented in the EMR)
- Renal replacement therapy required at enrollment (Yes/No)
- Vasopressors required at enrollment (Yes/No)
- Score on ordinal scale at enrollment (Hospitalized on low flow supplemental oxygen; Hospitalized on high flow supplemental oxygen; Hospitalized on non-invasive ventilation)

Subsequent to characterizing the cohort at baseline, we will explore and describe the outcome variables overall and grouped by study arm. We will take the same approach as for the cohort descriptors, using comprehensive summary statistics and graphical representations as appropriate. For depicting clinical course, alluvial or Sankey plots maybe be used.

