Subgroup analyses and differential treatment effects

To determine whether effects of treatment depend on any of the baseline characteristics, we will test the interaction between the characteristic and treatment effect in the PO model. Only if it is significant will we conduct a separate subgroup analysis. In this case, we will be liberal when considering whether a potential effect modifier has an interaction with the treatment, using a p-value of <0.2 . For continuous variables, of which age is the primary variable of interest, we will not create artificial groups but instead we will present the partial effect plots demonstrating how the treatment effect changes over age. If warranted, a subgroup analysis may be conducted using the same model as for the primary outcome, but with the subgroup-defining variable removed from the model. We will not adjust subgroup analyses for multiplicity, but all data reports will clearly indicate the potential for false positive findings. We will focus these subgroup analyses on estimates of potential group specific effects rather than significance testing. Any findings will be subject to further confirmatory studies. Subgroup analyses will be performed using the intention to treat sample.

Summary

The analyses described here are those necessary to answer the trial's primary question of whether advising patients to prone is more effective than usual care in improving clinical status five days after being hospitalized for Covid-19 with requirements for supplemental oxygen. Beyond our analysis exploring the effect of treatment on primary, secondary, and exploratory endpoints, we expect there to be multiple additional exploratory analyses conducted, in particular as they relate to the supplementary study and understanding the association between objective measures of proning and moment-to-moment oxygen levels. It is not possible to predetermine the nature of such analyses. However, we are committed to preserving rigor and reproducibility and will pre-specify each subsequent analysis in the context of the specific question to be answered, cognizant of bias and missingness in the data.

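### Separate subgroup analyses are run only where an interaction reaches p<0.2, over an unlisted set of characteristics, so the subgroup estimates the SAP intends to emphasise are selected for being large

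*SAP*

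**What the plan says.** The rule is in the SAP section on subgroup analyses and differential treatment effects.

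- **Purpose and scope.** Interactions with treatment are tested in the proportional odds (PO) model "To determine whether effects of treatment depend on any of the baseline characteristics". No list is given for this purpose. The nearest one, under Descriptive Analysis, is open-ended: "At a minimum, the following baseline variables will be described".
- **Gate.** "Only if it is significant will we conduct a separate subgroup analysis". The SAP adds that "we will be liberal when considering whether a potential effect modifier has an interaction with the treatment", "using a p-value of <0.2". A later sentence makes the analysis discretionary as well, to be done where warranted.
- **Continuous modifiers.** Age is named as the main one. These variables are not cut into groups but shown as partial effect plots.
- **Reporting.** "We will focus these subgroup analyses on estimates of potential group specific effects rather than significance testing". There is no multiplicity adjustment. Reports are to warn of possible false positives, and findings are to await confirmatory studies.

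The Main Analysis section says of the PO model's covariates: "Duplication of comorbidity variables will be avoided; only the Elixhauser score will be used". The SAP does not say whether this also limits which characteristics are tested for interaction.

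**The concern.** The section's aims conflict. It puts estimates ahead of tests, but a test decides which separate subgroup estimates are produced. An interaction passes only if its estimate is far enough from zero, and the same data then supply the estimate that is reported. So the reported contrasts are too large on average, and their nominal 95% intervals cover too rarely.

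At stake is how the subgroup results are read. Even if the effect of advising patients to prone were the same in everyone, the report could well show one kind of patient who seems to benefit and another who does not, without comparable subgroup results for the characteristics that were not flagged.

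**Working it through.** **Inputs**

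- Threshold p<0.2 (SAP, subgroup section). Taken as two-sided, so |Z| > 1.2816.
- Number of tests: not stated, so three counts are used. The Descriptive Analysis list has 19 entries if every item is counted. Removing duplicates as the Main Analysis section does leaves 10: age, sex, BMI, race, ethnicity, Elixhauser score, smoking, renal replacement therapy, vasopressors and baseline severity. Seven of these are categorical (all but age, BMI and Elixhauser).
- Precision: OR 1.6 with 80% power at 500 patients in total (protocol section 8; SAP, Population and Design Considerations). Planned enrolment is 550. Two-sided alpha of 0.05 is an assumption; the documents do not state it.

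**1. The plan's own figure.** Whitehead's formula is N = 12(z₁₋α/₂ + z_power)² / [(ln OR)²(1 − Σp̄³)]. The planning distribution in protocol section 8, best to worst, is 40/10/30/14/5/1%. An OR of 1.6 toward better outcomes gives 1 − Σp̄³ = 0.880, so

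N = 12 × 2.8016² / (0.4700² × 0.880) ≈ 485.

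At N=500 the power is 81.2%. The stated figure is reproduced closely. Other ways of setting up the distribution give 463 to 530, and the interim distribution actually used is not given.

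**2. Chance flags.** With no true effect modification, k independent tests give 0.2k expected flags, and P(at least one) = 1 − 0.8ᵏ.

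| Tests (k) | Expected flags | P(≥1) | P(≥3) |
|---|---|---|---|
| 7 | 1.4 | 79% | 15% |
| 10 | 2.0 | 89% | 32% |
| 19 | 3.8 | 98.6% | 76% |

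Many of the 19 entries overlap (BMI with obesity class; Elixhauser with the single conditions). Correlation leaves the expected count unchanged but alters the probabilities.

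**3. Size of what passes.** With no true interaction, the mean |Z| among flagged tests is 2φ(1.2816)/0.2 = 2 × 0.1755/0.2 = 1.755. Without a gate it is √(2/π) = 0.80, so the gate inflates it by 1.755/0.80 ≈ 2.2 times.

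**4. On the OR scale, for an illustrative two-level 50/50 modifier at N=550**

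- SE of the overall log OR: (0.4700/2.8016) × √(500/550) = 0.160.
- SE of the interaction: 0.160/√(0.5 × 0.5) = 0.320.
- Average ratio of ORs given a false flag: exp(1.755 × 0.320) ≈ 1.75. (At N=500 it is 1.80, against 1.31 without the gate.)
- Half the contrast falls on each side: exp(1.755 × 0.160) = 1.324. A uniform OR of 1.3 then looks like 1.3 × 1.324 = 1.72 in one half and 1.3/1.324 = 0.98 in the other.

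**5. Coverage of nominal 95% intervals, given a false flag**

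- Interaction: (0.20 − 0.05)/0.20 = 75%.
- Each subgroup log OR, 50/50 split: about 83%. For a 20/80 split it is 76% in the smaller group and 90% in the larger.

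**6. Real interactions.** At N=500, with a 50/50 split, a true ratio of 1.2 averages 1.60 when selected and has the wrong sign 13% of the time. A true 1.5 averages 1.96, and a true 2.0 averages 2.27.

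**The case against.** The best defence is that testing the interaction first is a deliberate and disclosed choice. It avoids running within-subgroup tests everywhere. The section also plays down significance, promises a false-positive warning and asks for confirmation. These safeguards are real, but they concern whether a finding is true. They do not tell readers that its size is inflated, and they do not shrink it.

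Several stronger readings are tempting, and the documents do not support them.

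- **That several spurious subgroups are certain.** The count depends on how many characteristics are tested, which the SAP does not state. Three or more flags has a probability of 15% to 76% across the counts above, and only if no true modification exists.
- **That every subgroup effect, including age, is gated.** Partial effect plots for continuous variables are not clearly tied to p<0.2, so for age, BMI and Elixhauser the plan may already show ungated results.
- **That single comorbidities are tested with no main effect in the model.** Nothing says they will be tested singly.
- **That unflagged characteristics leave no result at all.** Only the separate subgroup analysis is withheld. The SAP does not say that unflagged interaction estimates go unreported.
- **That the intervals fail altogether.** The 75% applies to the interaction; the group-specific intervals that the SAP emphasises do better, at about 83% in the 50/50 case.

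It also stands that the 50/50 split is an illustration. The documents give no prevalences, and race, smoking status and baseline severity can have more than two levels.

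**Conclusion.** The concern holds for the separate subgroup analyses. Followed as written, the rule selects on the same data that it then estimates from, and inflates the surviving contrasts about 2.2-fold in |Z| when there is no true modification. Even on the narrowest count of 7 variables, at least one chance flag is more likely than not, given independent tests. Tightening the threshold would not cure this: a 0.05 gate would pass only 0.5 to 0.95 chance findings over 10 to 19 tests, but those that passed would be larger still.

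The OR-scale figures rest on a 50/50 two-level modifier, N=550, two-sided alpha of 0.05 and the stated design precision. The point concerns the reporting of subgroup results only. A reader should not infer that the primary analysis is compromised, because the gate plays no part in it. The change should be made, but it is not critical to the trial's main conclusion.

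**What to change.** Before analysis, the sponsor should name the candidate effect modifiers in the SAP; which ones is the sponsor's choice. For each, whatever its p-value, report:

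- the interaction estimate with its 95% CI; and
- the subgroup-specific ORs, or partial-effect plots for continuous variables, from one PO model on the full intention-to-treat sample that includes the characteristic's main effect.

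Drop the p<0.2 gate and the separate subgroup refits. Label any other characteristic post hoc. Keep the false-positive warning and the call for confirmation.

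The cost is SAP wording only, with no new data. The downsides are a longer table that includes null subgroups, and fewer characteristics screened. In return, the plan would deliver the focus on estimation that it already states.
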